After data collection at six months, for each individual participant, the participant will immediately begin the second phase of the study when they will be randomized, using block randomization, to a placebo or a study drug group at the end of the 6-month visit to NIH. The allocation scheme is computer-generated using random permuted blocks to maintain balance of the two groups (placebo and control) and to maintain balance between children and adults. The participant will be randomized to the study drug or placebo group by an NIH pharmacist, who is blinded to the allocation scheme. Study drug assignments are recorded by the pharmacist, to be revealed only after the study is complete. BioAdvantex Pharma will provide oral effervescent NAC capsules, (PharmaNac) as well as identically packaged placebo capsules so that participants will not be able to distinguish the treatment from placebo. The study drug group will receive 15mg/kg/day (no more than 1800 mg/day) for the first week. After the first week, subjects who weigh fewer than 50kg will receive 30mg/kg/day of NAC (no more than 2700mg/day) divided TID over a period of six months. To increase compliance, as the tablets are formulated as 900mg each, subjects who weigh greater than 50kg will receive 2700mg/day.

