retest analysis yields a poor correlation ($ICC < 0.40$), then the scales will not be used in the study since they are not primary outcome measures. However, if they yield moderate to high correlation, we will use the scales throughout the entire study.

Randomized, double-blind, placebo controlled, drug trial (Phase 2 of protocol):

Student's t test will be used to compare treatment to control groups. As mentioned in the Introduction, under "Summary", success of the trial will be defined as finding a significant difference in the primary oxidative stress measure of of urine 15-F2t-isoprostane between the treatment and placebo groups at the termination of the study (significantly decreased urine 15-F2t-isoprostane concentration in treatment group compared to placebo group). A sub group analysis will be performed on adults versus children given the difference in dosing. A paired t test will be used to compare subjects to their baseline values. A student's t test will be used to compare the difference in glutathione between 6 months and 12 months, between the two groups. General linear modeling will be used to control for possible confounders such as gender, age, and baseline values. Log transformed values may be used if there is no bell curve. We will use an alpha of 0.05 to determine significance.

We will use the Grounded Theory Method (GTM) of data analysis to analyze the semi-structured interview data. GTM methodically organizes unique individual experiences collected during interviews into comparable categories so that it becomes possible to find commonalities as well as variations in personal experiences. We use GTM because it is particularly effective for analyzing qualitative interview data and because it is rigorous. A GTM approach is appropriate when there is limited knowledge about a substantive area, such as the fatigue and quality of life of individuals with RYR1-related myopathy.

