--In a recent crossover trial, conducted in 36 individuals with low resting GSH concentrations, NAC supplementation (2 × 600 mg, twice daily, for 30 days) led to a 22% reduction in 15-F2t-isoprostane concentration and improved exercise performance (Paschalis et al. 2017). These findings are pertinent for this protocol as it has been demonstrated pre-clinically that RYR1-RM models have low resting GSH concentrations, and both 15-F2t-isoprostane concentration and improved exercise performance are being tested in our trial. Additional antioxidant clinical trials have also shown a beneficial effect of treatment on 15-F2t-isoprostane concentration. In particular, an α -tocopherol (vitamin E) antioxidant trial in smokers (n= 81 placebo; n= 82 vitamin E) demonstrated that consuming 400 IU vitamin E daily resulted in a statistically significant (21%) difference in corrected urinary F2-isoprostane concentration compared to placebo following 32-months treatment (Guertin et al. 2016).

In combination, these findings strengthen the rationale for using 15-F2t-isoprostane concentration as the primary outcome measure for this protocol in place of GSH. The sample size recalculation for 15-NR-0072 was therefore performed using 15-F2t-isoprostane data from our study. [name], Clinical Center Statistician, was unblinded for the sample size recalculation. All investigators remain blinded until the study is complete. [name] used the current study data on isoprostane levels from participants in the treatment vs. placebo groups to calculate the N required to complete the study. The N achieved was 182, which is not feasible in this rare disease population and the study is being closed to data analysis.

11. Human Subjects Protection

a. Subject selection

Subject selection will be equitable as much as possible due to the rarity of RYR1-related myopathy. All ages within the specified range, races, and both genders will be accepted. Individuals with a genetic mutation in *RYR1* will be prioritized to decrease the rate of screening failures. Individuals with a muscle biopsy showing central cores will be prioritized to decrease the variability in the sample.

Subject selection for healthy volunteers will be equitable.

b. Justification for inclusion of children

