Date: July 2, 2018

RE: Statistical Analysis Plan for Protocol 15-NR-0072 Antioxidant therapy in RYR1-related congenital myopathy

Primary outcome measures

Where to find data (variables) for the below analyses in locked excel files:

- 1) AE_Spreadsheet_Demographics_LOCKED_2018.3.29
- 2) Urinelsoprostane_6MWT_LOCKED_2018.3.29
- 3) PillCount_PlasmaRedox_SalivaFBI_SMOxidativeStressDCFH_LOCKED_2018.3.29

Descriptive statistics

- Assess data distribution (i.e. basic descriptive statistics) for demographics (sex, ethnicity, smoking_status, alcohol_consumption, age_month0, height_month0, weight_month0, bmi_month0)

- Assess data distribution for urine isoprostane (all variables)

- Assess data distribution for six-minute walk test (predicted_distance_walked_month0, min_6_distance_month0, predicted_distance_walked_month6, min_6_distance_month6, predicted_distance_walked_month12, min_6_distance_month12).

- Assess data distribution for skeletal muscle oxidative stress (all variables),

- If possible, also assess data distribution for plasma redox (GSH_GSSG_month0, GSH_GSSG_month6, GSH_GSSG_month12, CYS_CYSS_month0, CYS_CYSS_month6, CYS_CYSS_month12).

- Assess data distribution for pill count (percent_compliance_month12).

- Descriptive statistics (frequency, mean, median, SD, SEM, IQR, range) for all the above for entire cohort at baseline (month 0) for demographics.
- Repeat abovementioned descriptive statistics split by treatment group (NAC and placebo) at baseline.
- Assess the frequency of AEs by system organ class (System Organ Class (SOC) (AE only) and by Preferred Term (Preferred Term (AE only)).

Natural history phase analyses

During the natural history phase of the study (month 0 to month 6), we will take one look at the data prior to the final analysis with the following two approaches:

1. After 30 participants complete their baseline visit, we will compare their baseline outcome measure values against healthy controls. The mean values for the primary outcome measures (corrected 15-F2t-isoprostane concentration and 6MWT distance) will be compared against existing data for otherwise healthy individuals using summary independent t-tests and/or standardized mean difference (i.e. Hedge's g which is a measure of effect size between two means, weighted by n). This analysis will be repeated when all baseline visits are completed.

Null Hypothesis (H_0)

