In *RYR1*-RM myopathy patients, there will be no statistically significant difference in corrected 15-F2t-isoprostane concentration and/or corrected 15-F2t-Isop:PGF2 α ratio between NAC and placebo groups at month 12, after controlling for established *a priori* confounders.

Alternative Hypothesis (H₁)

At month 12, in *RYR1*-RM myopathy patients allocated to NAC treatment, there will be significantly decreased corrected 15-F2t-isoprostane concentration and/or 15-F2t-Isop:PGF2 α ratio compared to those allocated to placebo, after controlling for established *a priori* confounders.

2. Run a general linear model comparing month 12 6MWT total distance (min_6_distance_month12) between NAC and placebo groups controlling for baseline value. Run this model again controlling for established *a priori* confounders including age, sex, height. Variables that do not contribute significantly to the model may be removed.

Run this model again and control for one additional hypothetical confounder (post hoc): FVC % predicted.

Null Hypothesis (H₀)

In RYR1-RM myopathy patients, there will be no statistically significant difference in 6MWT total distance between NAC and placebo groups at month 12, after controlling for established *a priori* confounders.

Alternative Hypothesis (H₁)

At month 12, in RYR1-RM myopathy patients allocated to NAC treatment, there will be significantly increased 6MWT total distance compared to those allocated to placebo, after controlling for established *a priori* confounders.

Adverse Event Analysis

The 3 categories for AEs in the locked data are:

1. AE

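### No SAP treatment model includes the child/adult factor used in randomisation; secondarily, the 6MWT and secondary models adjust for a baseline value whose visit is not named

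*SAP*

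**What the plan says.** **Randomisation.** Protocol Section 4a assigns each patient "to a placebo or a study drug group at the end of the 6-month visit to NIH", using permuted blocks intended "to maintain balance between children and adults". Months 0 and 6 are therefore both pre-randomisation. Section 10a adds that "A sub group analysis will be performed on adults versus children", because dosing differs.

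**Treatment models.** In the SAP's intervention phase section, model 1 (isoprostane) adjusts for the pre-intervention value and is then re-run with age, sex, height, weight, BMI, smoking and alcohol. Model 2 says: "Run a general linear model comparing month 12 6MWT total distance (min_6_distance_month12) between NAC and placebo groups controlling for baseline value". It is re-run with age, sex and height, and its hypotheses are stated on that adjusted form. The secondary models use an open covariate list that includes a baseline value and age. All three allow non-contributing variables to be removed. None names child/adult, and the protocol's adults-versus-children subgroup analysis does not appear in the SAP.

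**Visit.** The descriptive section uses baseline "for entire cohort at baseline (month 0) for demographics" and lists 6MWT distance at months 0, 6 and 12.

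**Timing.** The SAP carries "Date: July 2, 2018". Its 6MWT data file is named "Urinelsoprostane_6MWT_LOCKED_2018.3.29". Protocol Section 10b states: "All investigators remain blinded until the study is complete".

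**The concern.** When allocation is balanced on a factor that predicts outcome, that factor has been removed from the chance differences between arms. A model that leaves it out still counts its variation as residual error, so the standard error is larger than the design requires. Age is only a partial stand-in: it is linear, absent from the first-run models, and removable. In a disease where the recalculated N of 182 was judged infeasible (Protocol Section 10b), precision already paid for by the design is worth keeping.

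The second matter is one of wording. The SAP names the 6MWT outcome variable exactly but not its covariate. Two analysts could fit different models to a primary outcome, and the data were already locked when the SAP was dated.

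**Working it through.** **1. The plan's own figure.** Protocol Section 10b assumes changes of 1.7 and 0, SDs of 2.34 and 2.80, two-sided alpha 0.05 and 80% power, and needs 38 per group. A noncentral-t calculation with Satterthwaite degrees of freedom gives power 0.798 at 37 and 0.809 at 38, so 38 reproduces. It rests on glutathione and uses no covariate, so this point leaves it unchanged.

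**2. Omitting child/adult.** The documents give no child/adult effect on 6MWT. Let *s* be the share of the variance left after the prior value that a child/adult step explains. In the first-run model, SE without factor / SE with factor ≈ 1/√(1−s). For s = 5, 10, 20 and 30% this is 1.03, 1.05, 1.12 and 1.20.

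Simulation assumptions: N = 76; 20, 30 or 38 children; blocks of 4 within stratum; prior-value correlation 0.8; ages 7-18 and 18-60; height rising with age in children; 8,000 runs per cell. The removal-rule column uses backward selection at p < 0.05 with 30 children and 6,000 runs. Entries are SE without / SE with the factor.

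| s | Re-run (age, sex, height) | After removal rule | First run |
|---|---|---|---|
| 5% | 1.002-1.003 | 1.011 | 1.03 |
| 10% | 1.009-1.012 | 1.020 | 1.06 |
| 20% | 1.028-1.034 | 1.041 | 1.12 |
| 30% | 1.051-1.060 | 1.069 | 1.20 |

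In the re-run without the factor, type I error is 0.046-0.051 and the power loss is 0-5 points. After the removal rule the loss is about 1-5 points (for example 0.745 against 0.796 at s = 30%). If the factor has no effect, the re-run ratio is 0.995, so including it costs about 0.5%.

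A separate simulation without age (38 per arm, half children) shows the direction of the error. With a residual child/adult difference of 0.5 SD, type I error is 0.044 and power is 0.772 against 0.791. At 1.0 SD, type I error is 0.029 and power is 0.712 against 0.787. The test becomes conservative, not liberal.

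**3. Which visit the text supports.**

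- *For month 6:* The SAP intervention section is headed as running from month 6 to month 12. Its first bullet labels month 6 as pre-intervention and includes 6MWT. Protocol Section 10a takes the glutathione change from 6 to 12 months, and its next sentence has the linear model control for baseline values. The SAP's secondary intervention bullet compares arms on baseline values of all secondary outcomes, parallel to the month-6 bullet for the primaries. Those outcomes include DCF, which has no month-0 value, and the Aim 1 natural-history text also applies baseline to DCF.
- *For month 0:* The descriptive section dates baseline as month 0. The Aim 2 natural-history comparison contrasts baseline with 6 months.

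**4. If month 0 were used.** Variance ratio = (1 − r(0,12)²)/(1 − r(6,12)²). Power = Φ(2.8016/√ratio − 1.96), starting from an assumed 80% with month 6. The documents give no correlations or 6MWT power, so these are illustrations.

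- Both visits equally predictive: ratio 1.00, no loss.
- r(6,12) = 0.80, made up of stable 0.60 plus 0.25 decaying at 0.8 per six months, the remaining 0.15 being visit noise: r(0,12) = 0.60 + 0.25 × 0.64 = 0.76. Ratio = 0.4224/0.36 = 1.17, power about 73%.
- r(6,12) = 0.80, stable 0.60, the rest decaying without noise: r(0,12) = 0.70. Ratio = 0.51/0.36 = 1.42, power about 65%.
- Pure AR(1) decay: ratio = 1 + r². For r = 0.80 and 0.90 it is 1.64 and 1.81, power 59% and 55%.

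With either visit fixed in advance, simulated type I error stays at 4.7-5.3%.

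**The case against.** The strongest reply is that both parts are small. Age is in both primary re-runs and in the secondary list, which is open, and the 6MWT hypotheses are stated on the adjusted model. The protocol also plans an adults-versus-children subgroup. On the month-6 reading, which the intervention-phase text favours, the covariate costs nothing. Isoprostane alone defines success, and its model already uses the pre-intervention value. All of this stands, and it limits the point to a modest gain in precision plus a clarification. It does not remove the point: the first-run models contain no age, age may be dropped, and a subgroup analysis is not a model term.

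A reader might infer three stronger things.

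- *That leaving out the factor invalidates the comparison.* With complete data it does not; the error is on the conservative side. Dropout that differed by arm and stratum could introduce bias, but the documents do not show that.
- *That the visit was, or will be, chosen by result.* Fitting both visits and reporting the smaller p-value would give a type I error of about 7-9% under assumed correlations. Nothing in the documents suggests this. A SAP dated after data lock is not a SAP written after unblinding, and the protocol says investigators stay blinded, with one statistician unblinded for the sample size recalculation.
- *That a large power loss is built in.* This requires the month-0 reading and correlations that decay with little visit-to-visit noise. Neither is established.

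**Conclusion.** The point holds as one of efficiency and wording. The SAP omits the factor on which randomisation was balanced. With complete data this makes the standard error too large without bias or inflated type I error. Under the assumed effects the excess is about 0-6% in the 6MWT re-run, 1-7% after the removal rule, and up to about 20% only in the first-run model with a large child/adult step. The undated covariate most likely means month 6, in which case nothing is lost. If month 0 were used, the variance ratio could lie anywhere from 1.0 to about 1.8, depending on correlations the documents do not give, with no bias provided the visit is fixed in advance. The isoprostane success criterion and the target of 76 completers are unaffected.

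**What to change.** 1. Include the child/adult factor, as randomised, in every treatment model except DCF, where biopsies are adults only. Take it from the allocation record, releasing the stratum only: the SAP lists age only at month 0, and a patient may turn 18 before randomisation at month 6.
2. In model 2, replace the undated term with `min_6_distance_month6`. In the secondary models, specify the month-6 value and name the variables.
3. Exempt the child/adult factor and the prior-value term from the removal rule.
4. If treatment codes are already open, keep month 6 as the main covariate, on the ground that the SAP itself labels month 6 as pre-intervention. State that this was clarified after unblinding. Report the month-0 model and the model without the child/adult factor as labelled sensitivity analyses.

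The cost is a few lines of SAP text and one degree of freedom. No new data are needed: the month-6 6MWT variable is already listed, and the protocol's planned subgroup analysis already requires the child/adult classification.

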2. UP/SAE
3. Non-UP/SAE

The other categories do not apply as they are not AEs.

Please use these categories in column F: "IRB determination of category".

Exclude HVs (healthy volunteers) and only use RYR numbers. Exclude RYR023 and RYR024.

For the remaining AE events (i.e. in the 3 categories delineated above) all have individual RYR IDs.

Assess:

1. Which AEs occurred in NAC group and which occurred in Placebo group (descriptive statistics) (see attached p.1 Mock Table 1)

2. Were there more specific AEs (by preferred term, Column H on excel) of any kind in NAC vs. Placebo groups? Or were AEs equally distributed between groups? Both Chi-square test and Fisher's exact test extended to general RxC tables, aka the Freeman-Halton test, will be used to compare AE frequencies between NAC and Placebo groups.
3. For those in NAC group, what was event causality (see AE excel column Q) and what was event severity (AE excel column R)? (for an example of this table, see p. 7 of attached, first table on p. 7). Capture the "body system" from our AE excel column G (AKA "system organ class").

Secondary Outcome Measures

Natural History Phase (month 0 to month 6):

Aim 1: plasma GSH:GSSG ratio; plasma CYS:CYSS ratio, (corrected DCF-fluorescence intensity (month 6 only))

1. We will compare baseline outcome measure values against healthy controls, when possible, using a summary independent t-test (or non-parametric equivalent). Hedge's g will be used to assess standardized mean differences between *RYR1*-RM and otherwise healthy population groups.

Null Hypothesis (H_0)

There will be no difference in mean plasma GSH:GSSG ratio; plasma CYS:CYSS ratio, or corrected DCF-fluorescence intensity, between *RYR1*-RM and otherwise healthy individuals.

Alternative Hypothesis (H_1)

Plasma GSH:GSSG, and CYS:CYSS ratios will be significantly decreased and corrected DCF-fluorescence intensity will be significantly increased in *RYR1*-RM myopathy patients when compared to otherwise healthy individuals.

2. We will compare baseline outcome measure values against values obtained at month 6 using paired t-tests (or non-parametric equivalent) to determine changes between 0 and 6-month visits for each outcome measure.

Null Hypothesis (H_0)

Plasma GSH:GSSG, and CYS:CYSS ratios and corrected DCF-fluorescence intensity will not change significantly between 0 and 6 months in *RYR1*-RM myopathy patients.

Alternative Hypothesis (H_1)

There will be a statistically significant difference between 0 and 6-month plasma GSH:GSSG, and/or CYS:CYSS ratios and/or corrected DCF-fluorescence intensity in *RYR1*-RM myopathy patients.

Aim 2: Timed function tests; Biodex; Myotools, MFM, MRI, PROMIS, FACIT, MFI, NeuroQoL scales.

1. We will compare baseline outcome measure values against healthy controls, when possible, using a summary independent t-test (or non-parametric

equivalent). When sufficient normative data is available, Hedge's g may be used to calculate the standardized mean difference between groups.

Null Hypothesis (H_0)

There will be no difference, in graded functional tests (time to completion); Biodex (fatigue indices); Myotools values (grip and pinch strength), MFM (D1, D2, D3 and total % of maximum score), MRI (intramuscular fatty infiltration), PROMIS (scale scores), FACIT (total score), MFI-20 (total score), NeuroQoL (scale scores), between *RYR1*-RM and otherwise healthy individuals.

Alternative Hypothesis (H_1)

In *RYR1*-RM patients, graded functional tests (time to completion); Biodex (fatigue indices); Myotools values (grip and pinch strength), MFM (D1, D2, D3 and total % of maximum score), PROMIS (scale scores), FACIT (total score), NeuroQoL (scale scores) will be significantly lower and MRI (intramuscular fatty infiltration), MFI-20 (total score) significantly higher when compared to otherwise healthy individuals.

2. We will compare baseline outcome measure values against values obtained at 6 months using paired t-tests (or non-parametric equivalent) to determine changes between 0 and 6-month visits for each outcome measure.

Null Hypothesis (H_0)

Graded functional tests (time to completion); Biodex (fatigue indices); Myotools values (grip and pinch strength), MFM (D1, D2, D3 and total % of maximum score), MRI (intramuscular fatty infiltration), PROMIS (scale scores), FACIT (total score), MFI-20 (total score), NeuroQoL (scale scores), will not change significantly or clinically between 0 and 6 months in *RYR1*-RM myopathy patients.

Alternative Hypothesis (H_1)

There will be a statistically significant and/or clinically meaningful difference between 0 and 6-month graded functional tests (time to completion); Biodex (fatigue indices); Myotools values (grip and pinch strength), MFM (D1, D2, D3 and total % of maximum score), PROMIS (scale scores), FACIT (total score), NeuroQoL (scale scores), MRI (intramuscular fatty infiltration), MFI-20 (total score) in *RYR1*-RM myopathy patients.

3. Additionally, the following will be analyzed:

Optimal measures for fatigability in *RYR1*-RM will be determined using paired t-tests for 6MWT distance and speed, time for graded functional tests, and fatigue index for biodex fatigue test.

Spearman rho correlation, Pearson correlation and/or Bland Altman analysis will also be used to examine the relationship between slow vital capacity and forced vital capacity (L and % predicted). Descriptive statistics and change between baseline and 6 months will be assessed for FVC and SVC (L and % predicted).

Reliability will be assessed for PROMIS, FACIT, MFI, MFM, and NeuroQoL by Cronbach's alpha for internal consistency and by Intraclass correlation coefficient for test-retest.

Intervention phase analyses (intent-to-treat)

- Use an independent t-test (or non-parametric equivalent) to compare baseline values for all secondary outcomes above between NAC versus placebo groups. General linear modeling will be used to control for possible confounders such as such as but not limited to baseline values, gender, age, and baseline values. Log transformed values may be used if there is no bell curve. We will use an alpha of 0.05 to determine significance. Variables that do not contribute to the model may be removed.
- Using multiple imputation (x40 datasets and minimum/maximum value constraints from per protocol data) impute missing month 12 data.
- The following GLM should be run both *per protocol* and with ITT datasets.
- General linear model comparing month 12-month data between NAC and placebo groups (controlling for possible confounders such as but not limited to: baseline value, age, sex, height, weight, BMI, smoking status, alcohol status).

Exploratory Outcome Measures

Aim 1: Anaerobic threshold, NIRS; secreted ER calcium monitoring proteins (SERCAMP) assay in blood and muscle

Anaerobic threshold using NIRS will be evaluated for patterns in individuals with *RYR1*-RM compared to healthy controls. From this evaluation, the tissue saturation index will be calculated as $TOI = [O_2-Hb] / Tot-Hb$. The rate of decline and rise in TOI will be compared to healthy controls. NIRS data will also be obtained during CPET and Biodex

testing and may be used to generate new hypotheses regarding oxidative metabolism in *RYR1*-RM.

SERcaMP levels will be tested in an exploratory fashion in patient-derived myotubes to assess whether Ca^{++} levels are normal in the sarcoplasm and/or cytosol. This will generate new hypotheses regarding Ca^{++} dysregulation in *RYR1*-RM.

Aim 2: CPET, EIM, salivary FBI, melatonin, cortisol and DHEA; QoL qualitative interview

Correlative analysis (Pearson correlation and/or Spearman rho) will be used to examine the linear relationship between subjective fatigue measures (FACIT and MFI) and the salivary biomarkers (FBI, melatonin, cortisol, DHEA) to the objective fatigability measures mentioned above, such as CPET. This data may be used to generate new hypotheses fatigue and fatigability in *RYR1*-RM.

The QoL interviews will be mined for common themes across participants. Interviews will also be mined for any comments about differences in QoL before and after treatment. This data may be used to generate new hypotheses regarding QoL in individuals with *RYR1*-RM.

All data may be used for additional exploratory analyses, particularly for the natural history phase of the study. These additional analyses which will not include or alter 12-month data/results of the intervention phase analysis. This is due to the rare nature of this disease and thus the substantial value of this data to contribute findings in this population.

[name], PNP-BC
NIH/NINR/TIB NIH/NINR/TIB
[name]
[name]
[name]
[contact]
E-mail: [contact]
